4.3. Data collection: tools and procedure

The data collection will take place during the months of March (pre-test) and June 2022 (post-test). At both times it will be done virtually, using a digital form. Participants will access this form through the project's web-app. The pre-test collection will be carried out after signing the consent and the post-test, after the educational intervention, that is, at 12 weeks.

At both moments, information will be collected related to personal, anthropometric, and behavioral variables (diet and physical activity), self-examination, knowledge related to risk factors and symptoms of breast cancer, perception of risk of developing breast cancer, and barriers to carry out. take actions to prevent it.

Additionally, after the educational intervention, satisfaction with the use of the web-app will be evaluated.

The information on the behavioral variables will be recorded using the Motiva.Diaf questionnaire. It includes 12 items that measure adherence to and motivation to carry out recommendations related to nutrition (questions 1 to 7) and physical activity (questions 8 to 12). Each item presents a Likert-type response format with a range from 0 (lack of motivation to make the recommendation) to 5 (intrinsic motivation). In addition, each separate recommendation can be interpreted dichotomously (makes=1 or does not make the recommendation=0). Finally, the synthetic variable adherence to healthy recommendations is elaborated as a result of scoring each item in its dichotomous interpretation (range 0=worst adherence to healthy recommendations to 12=greatest adherence to healthy recommendations).

The self-examination is carried out by means of the question, do you perform the breast self-examination once a month.

The information related to knowledge, risk perception and barriers with the MARA questionnaire. This questionnaire, specifically related to breast cancer, consists of 31 items that measure the following constructs: knowledge related to risk factors (9 items), knowledge related to signs and symptoms (9 items), perception of risk of developing breast cancer breast (6 items) and perceived barriers to carry out prevention strategies (7 items). Items related to knowledge have a score of 0 (error) and 1 (correct), therefore the range of scores, both for risk factors and for signs and symptoms, is between 0 and 9. The score of the other two scales is represented on a Likert-type scale ranging from 1

(totally disagree) to 5 (totally agree), the total perception score being between 6 and 30 points (the lower the score, the lower the perception of risk and the barriers between 7 and 35 points (the lower the score, the fewer perceived barriers).

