4.2. Study population

It will be made up of women belonging to the VII health area of the Principality of Asturias, aged between 25 and 45 years, without a previous diagnosis of BC.

All women who give written consent to participate in the study will be included. Those who: (i) do not have adequate physical or psychological characteristics to participate in the study will be excluded; (ii) do not have the means to regularly access the web-app that will be used to carry out the educational intervention; (iii) your contact by email is not possible.

The recruitment of women will be carried out, between the months of January and February 2022, by sending a letter of invitation to participate from the health area. A random sample of 361 women will be sufficient to estimate, with 95% confidence and an accuracy of +/- 5 percentage units, a population percentage that is expected to be approximately 75%. The percentage of necessary replacements has been predicted to be 20%.

The health area VII technician and member of the research team ([name]) will draw up a list of all the women likely to be included in the study. The members of the research team prepare a letter for each of the women and they will be sent from the management of Sanitary Area VII to the women by postal mail.

The letter contains a contact email to which they will write if they are interested in participating. The women will be answered as the emails are received and when we have obtained the necessary sample, the project will be explained in detail with an information sheet that they may have at their disposal and they will be given their consent informed, which they will sign by selecting the box "I wish to participate voluntarily" that will appear at the end of the consent. Finally, they will be asked for a username and password to access the web-app. In other words, the user or pseudonym to access the web-app will be selected by the woman herself.

The selected women will be distributed, in March 2022, between the intervention (IG) and control (CG) groups using the simple randomization method and with a 1:1 ratio.

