4.4. Educational intervention

The IG women will receive an intervention based on the use of a web-app with a duration of 12 weeks, which will be complementary to the preventive activities carried out in the health area. The CG participants will not have access to the web-app during the 12 weeks that the intervention lasts and will only receive the usual health care.

The design and evaluation of the intervention is based on the Behavior Change Wheel (BCW)⁸² model and the web-app will be used as the central axis of the same.

The web-app will consist of 6 sections: information related to BC risk factors; self-exploration; feeding; physical activity; news and community the risk factors section will be merely informative. It will collect information in relation to the modifiable and non-modifiable factors that increase the risk of developing this tumor.

The self-examination section will include information related to the signs compatible with the CM and an explanatory video on how to perform the examination of your breasts. This information will enable women to identify the symptoms and signs that are consistent with the onset of cancer.

The food will be subdivided into 3 sections: nutritionist; recipes; tips. A nutrition expert will provide information in the form of videos about the characteristics of a healthy diet. In the recipes section, information related to healthy recipes will be provided. Finally, the advice section will be included where information obtained from secondary sources will be provided.

The physical activity section will also be subdivided into 3 sections: your 30 minutes; routes; options in your environment. First, information will be provided about the importance of doing 30 minutes of physical activity a day, indicating "walking" as an essential activity. In addition, 4 videos will be included with routines that women can perform at home. The routes section will include links to the pages of the municipalities belonging to the VII health area where the routes that can be taken in the area appear. The last section will include the health assets that women can find in the basic health

area (parks, sports spaces, walks...) with basic information about the type of activity that can be carried out in each of them.

Links to resources related to any aspect that may be of interest to the participants will be uploaded in the news section.

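### The knowledge test is reached through the web-app that also holds content on the tested topics, and no content lock is stated for intervention women at the post-test: a minor gap, cheap to close

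*Combined protocol and SAP*

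**What the plan says.** On how the outcomes are collected, section 4.3 states "At both times it will be done virtually, using a digital form" and then "Participants will access this form through the project's web-app". The post-test is placed once the educational intervention is over, at week 12. No supervision, time limit or closed-book instruction is mentioned.

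On what is tested, section 4.3 describes two nine-item knowledge scales in the MARA questionnaire, one on risk factors and one on signs and symptoms. Each item scores 0 if wrong and 1 if right, so each scale runs from 0 to 9.

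On what the web-app holds, section 4.4 describes a risk-factor section: "It will collect information in relation to the modifiable and non-modifiable factors that increase the risk of developing this tumor". Of the self-examination section it says "This information will enable women to identify the symptoms and signs that are consistent with the onset of cancer".

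On access, section 4.2 has women choose their login at enrolment, before they are allocated: "Finally, they will be asked for a username and password to access the web-app". The only restriction stated anywhere is in section 4.4: "The CG participants will not have access to the web-app during the 12 weeks that the intervention lasts".

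**The concern.** A right/wrong score measures knowledge only if the answers are not at hand while the woman responds. Here the form and material on the tested topics are reached through the same platform, remotely, and the stated access rule applies to one arm only. If the content is still open at week 12, an intervention woman can leave the form, read the relevant section and return. A control who sees only the form cannot do that inside the app. Looked-up answers would then count as learning, in one arm only. Randomization does not protect against this, because the difference in access arises after allocation.

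The post-test knowledge score is used in three places: the between-arm comparison and the within-arm before/after comparison (section 3.2.2), and the regression on the post-intervention score (section 5). Knowledge is also named in the hypothesis (section 3.1). Adherence, self-examination, risk perception and barriers have no answer key, so look-up does not touch them.

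**Working it through.** **Reading the sections together**

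1. Route: the form is reached through the web-app at both time points (4.3).
2. Overlap: the app has content on both tested topics (4.3 against 4.4). The item wording is not given, so the overlap is shown by topic, not item by item.
3. Intervention arm at week 12: no sentence closes the content.
4. Control arm at week 12: the bar covers the 12 weeks and the post-test comes after them, so 4.3 and 4.4 can be reconciled. Neither section says what controls see when they log in for the post-test.

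**The plan's own figure**

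Section 4.2 gives 361 women for a single percentage of 75%, within 5 points, at 95% confidence, with 20% replacements:

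- 1.96² × 0.75 × 0.25 / 0.05² = 288.1
- 288.1 / 0.8 = 360.1, rounded up to 361, which matches.

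The 20% is therefore already inside 361. Completers per arm at 1:1: 361 × 0.8 / 2 = 144.

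**Illustration of size**

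The documents give no standard deviation for the knowledge scales, no look-up rate and no number of items gained. All three are assumptions here. Let a share p of an arm gain g items by look-up, with no true effect:

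- bias = p_I × g − p_C × g (I = intervention, C = control)
- arm variance = SD² + p(1 − p)g²
- standard error = √[(variance_I + variance_C) / 144]
- false-positive chance = probability that a two-sided Welch test at 0.05 rejects. Section 5 sets p ≤ 0.05 and does not state sidedness; two-sided is assumed.

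Worked cell, 20% of intervention women only, 2 items, SD 2.0: bias = 0.20 × 2 = 0.40. Variances are 4 + 0.2 × 0.8 × 4 = 4.64 and 4.00. Standard error = √(8.64 / 144) = 0.245. Ratio = 0.40 / 0.245 = 1.63, giving a rejection probability of 0.37.

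| Look-up, intervention vs control | Items gained | SD 1.5 | SD 2.0 | SD 2.5 |
|---|---|---|---|---|
| 20% vs 20% | 2 | 0.050 | 0.050 | 0.050 |
| 10% vs 5% | 1 | 0.059 | 0.055 | 0.053 |
| 20% vs 15% | 2 | 0.079 | 0.068 | 0.062 |
| 10% vs 0% | 1 | 0.086 | 0.070 | 0.063 |
| 20% vs 10% | 2 | 0.175 | 0.125 | 0.100 |
| 20% vs 0% | 2 | 0.560 | 0.370 | 0.262 |

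Simulating the 0-9 ceiling (underlying mean 5 to 7, 20,000 trials per cell) lowers the one-arm results slightly: 6-8% for 10% gaining one item, and 19-53% for 20% gaining two. What drives the result is the difference in look-up between arms. When that difference is 5 percentage points, the chance stays at 5-8%.

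**The case against.** The strongest reply is that the plan already places the post-test after the intervention. The intervention lasts 12 weeks and the form follows it, so the content period can naturally be read as over. In addition, the questionnaire is not among the six app sections listed in 4.4, so reaching it through the app may mean no more than a login page that opens a form. This stands as a possible reading. It is why the finding is an exposure and not a demonstrated fault. But the text does not say that access ends or that the form stands apart from the content.

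Second, every participant is online and the form is remote, so anyone in either arm can search the web. This also stands. Equal look-up largely cancels, and only in-app look-up beyond what controls can do elsewhere is removable.

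Third, the figures can be made negligible or large by choice of inputs. That is correct, and no weight is put on any single one.

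A reader might also infer three stronger things that the documents do not support:

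- That the knowledge result will be biased, or that 26-56% is the expected error rate. That range needs 20% of intervention women to gain two items and no control to gain any; nothing in the plan sets those rates.
- That 4.3 and 4.4 contradict each other on control access. The bar ends before the control post-test, so they can both hold; what is missing is the view controls get.
- That content opens to controls before they answer, which would dilute the difference. No section says so.

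**Conclusion.** The point holds as a minor one. As written, the plan leaves open a look-up route at the post-test that may differ by arm and that favours the intervention on the two knowledge scales. Whether it exists in practice depends on two unstated facts: whether content stays open to intervention women at week 12, and whether controls see only the form. The size cannot be derived from the documents. On assumed SDs of 1.5 to 2.5 and 144 completers per arm, the false-positive chance runs from 5% with equal look-up to 26-56% in the most unequal case examined. Knowledge is one of several specific objectives, and the plan does not designate it as primary. The case for acting rests on the low cost of closing the route.

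**What to change.** Amend sections 4.3 and 4.4 to state that:

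- both arms complete each form by the same content-free route, either an individual emailed link or a form-only login;
- the educational sections are locked for each woman until her form is submitted;
- content is opened to controls, if at all, only after their post-test is in.

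This also settles how sections 4.3 and 4.4 fit together on control access. If a form-only view for controls is already intended, one sentence covers that part, and the lock for intervention women still needs adding.

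The cost is an access setting or an emailed link, plus two or three sentences of text. Email is already workable for everyone, since section 4.2 excludes a woman if "your contact by email is not possible". The sample size does not change. The downside is a brief content lock for intervention women at week 12. Protection is partial: web search, saved material and reading the app just beforehand all remain possible.

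### The post-test is reached only through the web-app that is also the intervention, so the two arms' completers can be selected differently and the comparison biased

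*Combined protocol and SAP*

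**What the plan says.** All from the combined protocol and SAP.

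- **Section 4.3, mode and route.** Of the two assessments: "At both times it will be done virtually, using a digital form". Then: "Participants will access this form through the project's web-app". The information collected at both times covers personal and anthropometric data, diet and physical activity, self-examination, knowledge, risk perception and barriers.
- **Section 4.3, timing.** The form is completed again at "the post-test, after the educational intervention, that is, at 12 weeks".
- **Section 4.4, intervention arm.** "The IG women will receive an intervention based on the use of a web-app with a duration of 12 weeks".
- **Section 4.4, control arm.** "The CG participants will not have access to the web-app during the 12 weeks that the intervention lasts".
- **Section 4.2, contact.** A woman is excluded if "your contact by email is not possible", so the team can email every participant. Each woman chooses her own username or pseudonym and a password for the web-app.
- **Section 4.2, losses.** A single overall allowance of 20% for replacements, not divided by arm or by app use.

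No section describes another route to the post-test, or reminders. Section 5 names no analysis set, missing-data method or sensitivity analysis.

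**The concern.** Outcome measurement runs through the thing being tested. In the intervention arm, a regular user is already where the form is, while a woman who gave up early must come back to the app in June to be measured. Response can therefore depend on engagement. In the control arm it cannot depend on engagement with the app content, because there was none. Control women must instead enter an app that has been closed to them for 12 weeks, which is a different reason for loss.

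Randomisation balances the women allocated. It does not balance two sets of completers produced by different processes. The main objective in section 3.2.1 is the effectiveness of the intervention. If intervention completers over-represent engaged users, the comparison moves towards the effect in women who kept using the app. Every outcome on the form is exposed, and section 5 contains nothing that would correct it. The regression there models a post-intervention score that unmeasured women do not have.

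**Working it through.** **1. The plan's own figure.** Section 4.2 gives 95% confidence, ±5 points, an expected 75% and 20% replacements.

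n = 1.96² × 0.75 × 0.25 / 0.05² = 288.11; 288.11 / (1 − 0.20) = 360.1, rounded up to 361.

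This matches the stated 361, so the 20% works as a loss allowance: 0.20 × 361 ≈ 72 women without data. It says nothing about who they are.

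**2. Limiting case (assumed).** A fraction m of intervention women stop, gain nothing and are all lost. Everyone else gains d and responds. Control loss is unrelated to outcome.

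- Effect in all randomised women: (1 − m)d
- Effect in completers: d
- Ratio: 1/(1 − m) = 1/0.90 = 1.11 at m = 10%; 1/0.80 = 1.25 at m = 20%

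**3. Softer case (assumed).** Let e be the engaged share of the intervention arm, r1 and r0 the post-test response in engaged and disengaged women, and R = e·r1 + (1 − e)·r0 the overall response. Fix R = 0.80, borrowing the plan's 20% for illustration, and r0 = 0.60. Then r1 = (0.80 − (1 − e) × 0.60)/e, and the engaged share of completers is e·r1/0.80. If only engaged women benefit, the effect ratio is that share divided by e, which is r1/0.80.

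| e | r1 | Engaged share of completers | Effect ratio |
|---|---|---|---|
| 50% | 1.000 | 62.5% | 1.25 |
| 60% | 0.933 | 70.0% | 1.17 |
| 70% | 0.886 | 77.5% | 1.11 |
| 80% | 0.850 | 85.0% | 1.06 |

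A stronger gradient, r0 = 0.40 with e = 70%, gives r1 = 0.68/0.70 = 0.971 and a ratio of 0.971/0.80 = 1.21. Since r1 cannot exceed 1, the ratio at 20% loss cannot exceed 1/0.80 = 1.25 under these assumptions. With r1 = r0 = 0.80 the ratio is 1.00: no bias.

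**4. No true effect (assumed).** The ratios above only scale a real effect. Suppose instead that the app does nothing and engaged women have a prognosis 0.5 SD better. With 180 randomised and 0.80 × 180 = 144 analysed per arm, and control loss at random, the bias is (engaged share of completers − e) × 0.5 SD:

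- e = 50%: 0.125 × 0.5 = 0.0625 SD
- e = 80%: 0.05 × 0.5 = 0.025 SD

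The standard error is √(2/144) = 0.118 SD. The two-sided error at a nominal 5% is 1 − Φ(1.96 − b/SE) + Φ(−1.96 − b/SE), about 8.3% and 5.5% respectively. Section 5 does not state sidedness; two-sided is assumed.

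**5. Control arm.** The net bias is the intervention-arm shift minus the control-arm shift. If control completers were also better-prognosis women by 0.0625 SD, the largest bias in step 4 would cancel. The documents give no figure for this.

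**The case against.** The strongest case against is that the harm is inferred. No section gives app use or response by app use. Both arms have the same stated form route, and section 4.2 asks participants for their own login. Section 4.3 does not say how women are prompted in June, so an email prompt leading to a login is compatible with the text. Control women who return after 12 weeks may be the more motivated ones, which would pull the contrast towards no difference. An emailed link may also be ignored by the women who ignored the app.

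Most of this stands as a limit on the claim, and it rules out four stronger readings:

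- *That women who stop are the least likely of all to be measured.* The argument supports this only within the intervention arm. Control loss could be as high or higher.
- *That the effect is necessarily inflated.* This needs control loss to be unrelated to outcome, which the documents do not establish. For risk perception, the plan does not say which direction counts as benefit.
- *That controls cannot complete the post-test.* Section 4.4 closes the app during the 12 weeks, and the post-test follows the intervention, so the two sections can both hold. How controls then reach the form is not explained.
- *That the plan rejects email for prompting.* It is silent.

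What does not stand is that a shared route removes the problem. The same login can select differently in women who have been offered the app content for 12 weeks and women kept from it.

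**Conclusion.** The concern holds as a risk of differential selection, not as a demonstrated bias. The premise is explicit in sections 4.3 and 4.4: the only described route to the post-test is the app that is also the intervention. The likely direction is towards a larger apparent effect if control loss is unrelated to outcome; otherwise the net direction cannot be determined.

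The size is modest under the assumptions shown. At 20% intervention-arm loss the completer effect is about 1.06-1.25 times the all-randomised effect, and 1.25 is the ceiling under those assumptions rather than an expected value. If there is no true effect, a false-positive rate of about 5.5-8.3% needs the further assumption of a 0.5 SD better prognosis in engaged women. Equal response by engagement, with control loss unrelated to outcome, gives no bias. The point is worth acting on because prevention is cheap and outcomes that were never collected cannot be recovered in the analysis.

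**What to change.** In section 4.3, replace the web-app route for the post-test with wording such as: *At 12 weeks every randomised woman in both groups will be sent an individual email link that opens the post-test form without entering the web-app content. The number and timing of reminders will be the same in both groups, regardless of use of the web-app. Post-test response will be reported by group.*

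The cost is small. Email contact is already a condition of entry, and only a form link and a reminder schedule are needed. The downside is that the link must carry the woman's existing pseudonym or a code so that pre-test and post-test can be matched. This has to be set up in line with the confidentiality commitment in section 6. As the project is already ethics-authorised, the team should check whether the change needs to be notified.

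The change makes measurement less dependent on app use. It does not eliminate engagement-related loss, which is why response by arm should be reported alongside it.

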3.2.2. Specific Objetive

- Evaluate adherence to behavioral recommendations before and after after the educational intervention for each group separately.
- To compare adherence to behavioral recommendations after the intervention between the intervention and control groups.
- Evaluate, in each group separately, the knowledge in relation to the risk factors and symptoms of breast cancer before and after the intervention.
- To compare the level of knowledge in relation to the risk factors and symptoms of breast cancer between the intervention and control groups before and after the intervention.
- Estimate the risk and self-perception of developing breast cancer before and after the intervention for each of the groups.
- To compare the risk and self-perception of developing breast cancer between the intervention and control groups after the educational intervention.

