5. STATISTICAL ANALYSIS

Initially, the normality of the distribution of the variables will be verified, the Kolmogorov-Smirnov test will be used. A description of the variables will be made using percentages, means (standard deviation) or median (interquartile range) depending on their nature and distribution.

To determine the association between variables, the chi-square test, McNemar for qualitative variables, will be used. For qualitative variables, they will be determined based on the distribution of variables.

Linear regression analyzes will be carried out to determine which variables best predict the score after the intervention in terms of knowledge about risk factors, signs-symptoms of early detection of breast cancer, knowledge and adherence to healthy behaviors.

The analyzes will be carried out using the IBM SPSS version 24.0®, considering that the results were statistically significant when the value of p is ≤ 0.05 .

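### Monthly self-examination and perceived barriers are measured twice but named in no objective; self-examination has only a generic chi-square to compare the arms, and barriers have no clearly assigned test

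*Combined protocol and SAP*

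**What the plan says.** Section 4.3 lists what is collected at both time points: "At both moments, information will be collected related to personal, anthropometric, and behavioral variables (diet and physical activity), self-examination, knowledge related to risk factors", followed by symptom knowledge, risk perception and barriers. The bracket after the behavioural variables confines them to diet and physical activity, and self-examination is a separate entry in the list. It is measured by one question: "The self-examination is carried out by means of the question, do you perform the breast self-examination once a month".

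The adherence score is built from Motiva.Diaf, of which the plan says: "It includes 12 items that measure adherence to and motivation to carry out recommendations related to nutrition (questions 1 to 7) and physical activity (questions" and then the numbers of the last five). Each item is scored 0 or 1 and the items are summed to a range of 0-12. Barriers are a separate MARA scale, "perceived barriers to carry out prevention strategies (7 items"), scored 7 to 35.

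Section 4.4 gives self-examination its own part of the app, with information on signs and "an explanatory video on how to perform the examination of your breasts".

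Of the six specific objectives in 3.2.2, the one closest to a behavioural comparison between arms is "To compare adherence to behavioral recommendations after the intervention between the intervention and control groups". The others concern adherence within each group, knowledge of risk factors and symptoms, and risk and self-perception.

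Section 5 says that "the chi-square test, McNemar for qualitative variables, will be used", without assigning either test to an outcome or time point. Its linear regressions take knowledge and adherence scores as outcomes.

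**The concern.** The app demonstrates a practice and the trial asks about it twice, yet no objective says how the answer will be judged. The adherence score contains no self-examination item, so an effect of the app on that practice alone could not appear in the planned adherence comparison. If the team later tests self-examination or barriers, no objective will show that the comparison was intended, and the decision to report it could follow the result.

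There is also a question of method. If chi-square is applied to the post-test answers, it yields a p-value but no estimate of how many more women examine themselves monthly. It also sets aside a pre-test answer to the same question that is already in the database.

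**Working it through.** **Where each measure appears**

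| Place in the plan | Self-examination (practice) | Perceived barriers |
|---|---|---|
| Collected pre and post (4.3) | yes, one question | yes, 7 items, 7-35 |
| In the 0-12 adherence score (4.3) | no: 7 nutrition + 5 activity = 12 items | no |
| Named in an objective (3.2.2) | no | no |
| Regression outcome (5) | no | no |
| Named test that can compare arms (5) | chi-square, generic | none clearly assigned |
| Named within-arm test (5) | McNemar, generic | none clearly assigned |

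The self-examination question is taken to have a yes/no answer, as its wording suggests; the response format is not stated. Collection in both arms is inferred from the reference to participants and from the between-group objectives.

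**The plan's own figure**

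Section 4.2 gives 361 women for 95% confidence, ±5 points, an expected 75% and 20% replacements.

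- n = 1.96² × 0.75 × 0.25 / 0.05² = 288.1
- 288.1 / (1 − 0.20) = 360.1, rounded up to 361

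The figure reproduces, and the 20% is already inside it. It sizes the precision of one unnamed percentage, not a comparison between arms.

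**Precision for self-examination**

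Women per arm after losses, with 1:1 allocation: 361 × 0.80 / 2 = 144.4, so about 144.

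The half-width of the 95% interval for the difference, with the same rate p in both arms, is 1.96 × √(2p(1−p)/144). With adjustment for the pre-test answer it is multiplied by about √(1−r²), where r is the pre/post correlation. This factor is a linear-model approximation applied to a binary outcome. The rates and correlations are assumptions.

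| p (assumed) | unadjusted | r = 0.3 | r = 0.5 | r = 0.7 |
|---|---|---|---|---|
| 0.3 | ±10.6 | ±10.1 | ±9.2 | ±7.6 |
| 0.5 | ±11.5 | ±11.0 | ±10.0 | ±8.2 |

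At p = 0.4 the unadjusted value is ±11.3. At r = 0.5 the gain equals 1/(1 − 0.25) = 1.33, or about 33% more women. No comparable figure is given for barriers, because the documents provide no standard deviation for that score.

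**The case against.** Four stronger readings are tempting, and the documents do not support them.

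- *The pre-test answer is ignored altogether.* McNemar is named, is a paired test, and would use that answer within each arm. The gap is confined to the comparison of intervention with control.
- *The trial plans no answer of any kind on self-examination.* A yes/no item is exactly what chi-square and McNemar serve, so a usable test exists. What is missing is an objective and a named comparison. The phrase about behavioural recommendations in 3.2.2 is undefined and could be stretched to include self-examination, and the main objective is generic. Section 4.3 makes that reading less likely, because its wording "behavioral variables (diet and physical activity), self-examination" keeps the two apart.
- *The barriers items go unused.* Section 5 plans a description of the variables without exclusions and looks for predictors of the post-test scores, so barriers may enter there. Its sentence on choosing tests by distribution refers to qualitative variables, but these are covered in the sentence before. It may be a slip for quantitative, in which case it would reach the barriers score, still without naming it.
- *The self-examination part of the app has no outcome.* Section 4.4 states its purpose as recognising symptoms and signs, and the 9-item signs-and-symptoms score covers that in the objectives and the regressions. Only the practice lacks an objective.

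Two further objections carry weight. Section 5 does not assign a between-arm test to any named outcome, and no primary outcome is designated, so this is one part of a wider gap that two secondary outcomes will not close. It is also a defensible choice of scope to treat self-examination and barriers as descriptive, since the hypothesis speaks of knowledge and risk behaviours. But the plan does not say that this is the choice made.

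**Conclusion.** The point holds as a modest improvement. That both measures are collected twice and lie outside the objectives, the adherence score and the regression outcomes follows directly from 3.2.2, 4.3 and 5. The missing objective alone would be little more than missing detail. The firmer part is the method: for self-examination, the one named test able to compare the arms gives no effect size and leaves out a baseline answer that costs nothing more to use.

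The gain in precision is illustrative. It runs from about half a point of half-width (r = 0.3) to about 3 points (r = 0.7), given about 144 women per arm, assumed rates of 30-50% and the linear approximation. It also assumes that women give the pre-test answer before they know their arm. The case for naming the outcomes does not depend on these figures.

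**What to change.** In 3.2.2, add monthly self-examination and perceived barriers as secondary outcomes, compared between the intervention and control groups at 12 weeks and reported whatever the result.

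In section 5, add two lines:

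- **Self-examination:** the intervention minus control difference in the percentage answering yes, with a 95% confidence interval, from a binomial model with arm and the pre-test answer. A standardised risk difference from logistic regression avoids the convergence problems that an identity link can bring.
- **Barriers:** the difference in mean score with a 95% confidence interval, from a linear model with arm and the pre-test score.

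Leave the 0-12 adherence score unchanged, so that the questionnaire is used as designed. If the team regards either measure as exploratory, a sentence saying so would settle its status.

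The cost is one objective and two lines of analysis, with no new data. The downside is two more comparisons, which should be labelled secondary.
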